#### SUMMARY

#### Rationale

Critically ill pediatric patients often need some form of ventilatory support. Remarkably, despite this worldwide use of mechanical ventilation, there is a lack of scientific evidence how these interventions can be applied most optimally. Much of the current clinical practice is based upon experience and data originating from critically ill adult patients. This probably explains the significant practice variability of ventilatory support. Following the introduction of new interventions, it is reasonable to assume that ventilatory support practices may have further changed and worldwide variances in ventilatory support could be substantial. We argue that it is imperative to understand how ventilatory support is currently being used to ascertain in which patient category existing or novel interventions may be considered to optimize ventilation strategies, and to support the development of clinical practice guidelines.

#### Objective

To a) describe the practice of ventilatory support in critically ill pediatric patients, b) to identify potentially modifiable ventilation setting and parameters that have independent associations with outcome including duration of ventilatory support, the number of days free from ventilatory support at day 28, length of ICU stay, and ICU mortality and c) to study the prevalence of the Pediatric Acute Respiratory Distress Syndrome (PARDS).

#### Study design

Investigator-initiated, prospective, international, multicenter observational cohort study over a 10-year period. Each year, data will be collected in two predefined 4-week periods, one in the winter season and one in the summer season. A third 4-week period will be in case of epi- or pandemics. Local investigators will capture data on demographics and baseline characteristics, ventilator settings and ventilation parameters, and outcomes in their hospital. Data collection is kept minimal to keep workloads associated with the study as low as possible.

#### Study population

Patients are eligible if (1) aged < 18 years; (2) admitted to an intensive care unit of a participating hospital; (3) for any (critical illness) necessitating ventilatory support for at least 12 hours. We exclude premature infants, i.e., patients with a postconceptional age corrected for gestational age < 37 weeks.

#### Main study endpoints

The primary endpoint is a set of key ventilation settings and ventilation parameters, including tidal volume (VT), peak inspiratory pressure (PIP), plateau pressure (Pplat), positive end-expiratory pressure (PEEP), inspired fraction of oxygen (FiO2), inspiration to expiration ratio (I:E), inspiration time, set respiratory rate, total respiratory rate, compliance (Crs), driving pressure ( $\Delta$ P) and the mechanical power of ventilation (MP). Secondary endpoints include the incidence of PARDS, duration of ventilatory support, the number of days free from ventilatory support at day 28, length of ICU stay, and ICU mortality. We will also determine whether there are potentially modifiable factors that have an independent association with outcome.

# Nature and extent of the burden and risks associated with participation, benefit and group relatedness

Prospective collection of demographic data, ventilation settings and ventilation parameters, and outcomes means the risks are negligible and the burden is minimal.

#### **1. INTRODUCTION AND RATIONALE**

#### 1.1. Practice of ventilatory support in children

Critically ill pediatric patients often need ventilatory support (1). Despite the worldwide use of this intervention and its lifesaving potential, studies on practice of ventilatory support in critically ill pediatric patients remain scarce. Various studies characterized practice of invasive ventilation in pediatric patients and reported significant variability (2, 3). However, these studies date back more than 10 years ago. Since new interventions have been introduced, it is likely that practice of ventilatory support have changed since then, and worldwide variances in ventilatory support could be substantial.

#### 1.2. Practice of ventilatory support in adults

Much of the current practice is based upon experience and data originating from studies in critically ill adult patients. These adult studies have shown substantial variation in ventilator settings and ventilation parameters, between different patient categories and also between geo–economic regions (4). These studies also showed that certain ventilation settings and ventilation parameters have independent associations with outcome, including tidal volume (VT), positive end expiratory pressure (PEEP), driving pressure ( $\Delta P$ ), mechanical power of ventilation (MP), and the fraction of inspired oxygen (FiO2) (5-18).

#### 1.3. Need for a new study

Studies on practice of ventilatory support in critically ill pediatric patients remain scarce and much of the current practice is based upon data originating from critically ill adult patients. However, findings of studies in critically ill adult patients may not be translatable to critically ill pediatric patients due to different lung physiology and different immune responses. For example, lung compliance differs between different age groups, also the extend of ventilator induced lung injury (VILI) might be age– dependent (19) and pediatric patients are more susceptible to the adverse effects of oxygen toxicity than adults (20-22). Randomized clinical trials are needed to investigate the effectiveness of various ventilator settings to improve practice of ventilatory support. However, before we can design such studies, we first need to understand worldwide clinical practice in critically ill pediatric patients. The here proposed study will give capture detailed data on ventilatory support. This allows us to determine which potentially modifiable factors have independent associations with outcomes, including duration of ventilatory support, the number of days free from ventilatory support at day 28, length of ICU stay, and ICU mortality. Since this study will run over a long period of time, and will include patients worldwide, we will be able to describe temporal changes and geo–economic differences.

#### 2. OBJECTIVES & HYPOTHESES

#### 2.1. Objectives

The aims of this study are to:

- describe the practice of ventilatory support;
- study temporal changes in practice of ventilatory support;
- study geo–economic differences in ventilatory support and outcomes in critically ill pediatric patients; and
- identify potentially modifiable factors that have independent associations with outcome including duration of ventilatory support, the number of days free from ventilatory support at day 28, length of ICU stay, and ICU mortality.

#### 2.2. Hypotheses

We will test the following hypotheses:

- practice of ventilatory support varies substantially; and
- potentially modifiable factors related to ventilation have independent associations with outcome in critically ill pediatric patients, including duration of ventilatory support, the number of days free from ventilatory support at day 28, length of ICU stay, and ICU mortality.

## 3. STUDY DESIGN

Investigator-initiated, prospective, international, multicenter, observational study in critically ill pediatric patients. This study will start in 2024 and will run for a period of 10 years.

#### 4. STUDY POPULATION

#### 4.1. Population (base)

Critically ill pediatric patients receiving ventilatory support.

#### 4.2. Inclusion criteria

Patients are eligible if:

- aged < 18 years;
- admitted to an intensive care unit (ICU) of a participating hospital during the period of data collection; and
- receiving ventilatory support > 12 hours.

### 4.3. Exclusion criteria

The following patients will be excluded:

premature infants (i.e., postconceptional age corrected for gestational age < 37 weeks).

### 4.4. Sample size calculation

To investigate the association of a limited set of pre-specified confounders with mortality in critically ill pediatric patients receiving invasive ventilation using logistic regression we estimate to need 100 events using the 10 event per variable of thumb. We aim to add 10 covariates to the model. With a conservative estimate of overall PICU mortality of 3% (1, 23) 3300 patients are needed for this analysis. With a conservative estimate of 50 participating centers, including 30 patients per inclusion period, the first analyses can be performed after the first year of inclusions. To explore differences between age groups (< 1 month, 1-11 months, 1-2 years, 3-6 years, 7-12 years, 13-18 years) and to do the same analysis in these groups we need around 19.800 patients in total. Taking a dropout of participating centers of around 30% into account, we expect to reach this sample size after including patients for eight years. After the first year, we will also start to include patients receiving other types of ventilatory support (i.e., noninvasive ventilation (NIV), high-frequency oscillatory ventilation (HFOV), continuous positive airway pressure (CPAP), bi-level positive airway pressure (BiPAP), and high-flow nasal oxygen (HFNO)). As some of these types, for example HFOV, are less frequently used and to be able to do the same analysis, we expect to need to include patients for approximately 10 years.

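### Section 4.4 promises the first mortality analysis after year 1, but its own inputs give 3,000 patients and 90 deaths against the 3,300 patients and 100 deaths it requires

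*Protocol*

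**What the plan says.** Protocol section 4.4 (Sample size calculation) builds the requirement in three steps. For the logistic model of mortality in invasively ventilated children, "we estimate to need 100 events using the 10 event per variable of thumb". The number of variables follows: "We aim to add 10 covariates to the model". The patient number comes from the death rate: "With a conservative estimate of overall PICU mortality of 3% (1, 23) 3300 patients are needed for this analysis".

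The section then turns to accrual. On what it calls a conservative estimate, it assumes "50 participating centers, including 30 patients per inclusion period, the first analyses can be performed after the first year of inclusions". The number of periods per year is in the Summary under Study design: "Each year, data will be collected in two predefined 4-week periods", one in winter and one in summer. A third period is added only in an epidemic or pandemic.

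For the same model in six age groups, section 4.4 asks for about 19,800 patients and adds: "Taking a dropout of participating centers of around 30% into account, we expect to reach this sample size after including patients for eight years". Section 7.4 (Planned analyses) says that an analysis is carried out once an adequate sample size for it has been reached. It gives no number.

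**The concern.** The requirement and the accrual forecast stand side by side in one section, so a reader will take the forecast as showing that year 1 delivers what the model needs. If it does not, a team following section 4.4 could fit the first mortality model below the events-per-variable rule that the protocol sets for itself. Section 7.4 would not clearly stop this, because the only figures that could define an adequate size are those in section 4.4, and that section says one year is enough.

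The eight-year forecast for the age-group analyses uses the same accrual inputs plus a 30% loss of centres, so it needs the same check.

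**Working it through.** **Inputs.** From section 4.4: 10 covariates, 10 events per variable, 3% mortality, 50 centres, 30 patients per inclusion period (read as per centre), six age groups, about 30% centre dropout. From the Summary: 2 scheduled periods a year.

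**Required sizes.**
- Deaths: 10 × 10 = 100.
- Patients: 100 / 0.03 = 3,333. The protocol's 3,300 is this figure rounded down, and gives 3,300 × 0.03 = 99 deaths. That is ordinary rounding.
- Six age groups: 6 × 3,300 = 19,800, as stated.

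The required sizes therefore reproduce.

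**Year-1 accrual, no dropout.**
- Patients: 50 × 30 × 2 = 3,000.
- Deaths: 3,000 × 0.03 = 90.
- Events per variable: 90 / 10 = 9.
- Shortfall: (3,300 − 3,000) / 3,300 = 9.1% of patients; 10 of 100 deaths.

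Reaching 3,300 from two periods would take 3,300 / (50 × 2) = 33 patients per centre and period, or 3,300 / (30 × 2) = 55 centres. Reaching 100 deaths from 3,000 patients would take mortality of 100 / 3,000 = 3.33%.

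**Time to close the gap.** Ten more deaths need about 10 / 0.03 = 333 patients. One further period brings 50 × 30 = 1,500 patients (45 deaths). With 30% of centres gone it brings 35 × 30 = 1,050 patients (31.5 deaths). Either is enough, so the 100th death is expected in year 2.

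**Eight-year accrual.** Full accrual is 3,000 a year; with 30% of centres gone it is 3,000 × 0.7 = 2,100. Section 4.4 does not say when centres leave, so several patterns were tried.

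| Pattern of centre loss | Patients after 8 years |
|---|---|
| None | 3,000 × 8 = 24,000 |
| 30% missing from the start | 2,100 × 8 = 16,800 |
| Full first year, then 30% lost | 3,000 + 7 × 2,100 = 17,700 |
| 30% lost at half-time | 4 × 3,000 + 4 × 2,100 = 20,400 |
| Linear to 30% by year 8, year-end values | 3,000 × (8 − 0.3 × 36/8) = 19,950 |
| Linear to 30% by year 8, mid-year values | 3,000 × (8 − 0.3 × 32/8) = 20,400 |
| Geometric to 30% by year 8 | sum of 3,000 × 0.7^(y/8), y = 1 to 8, = 19,740 |

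Gradual loss gives 19,740 to 20,400, in line with the stated 19,800. Loss from the start gives 16,800, and 19,800 would then take 19,800 / 2,100 = 9.4 years.

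**The case against.** The best defence is that the one-year figure is a forecast and not a calendar trigger. Section 7.4 ties each analysis to sample size, so if year 1 yields 3,000 patients the model simply waits. This largely stands, and it is why the harm is modest. It does not rescue the sentence in section 4.4, which says that year 1 suffices, and section 7.4 supplies no number of its own to override it.

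A second defence is that the protocol calls both the 50 centres and the 3% mortality conservative, so the real yield may be higher. That is possible: 55 centres or 3.33% mortality would remove the gap. But 3,300 was derived from that same 3%, and on the stated inputs it is not reached. A third inclusion period would lift year 1 to 50 × 30 × 3 = 4,500 patients, but it depends on an epidemic and cannot carry a planned milestone.

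Two stronger readings are tempting. A reader might infer that the eight-year figure is also wrong, because a flat 30% loss gives only 16,800. The documents do not support that. They never say that 30% of centres are absent from the first day, that reading sits badly with counting all 50 in year 1, and gradual loss reproduces the stated figure. A reader might also infer that the ten-year expectation for less common support such as HFOV cannot be met. That would require knowing whether the 30 patients per period count every type of support and what mortality applies to HFOV patients, and the protocol states neither.

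**Conclusion.** The year-1 statement does not follow from the plan's own inputs: 3,000 patients and 90 deaths are expected, against 3,300 and 100. This rests on reading 30 patients as per centre and period, on the two scheduled periods, on 3% mortality and on no centre loss in year 1. Early centre loss would make it worse: with 30% gone from the start, year 1 gives 2,100 patients and 63 deaths.

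The consequence is 9 instead of 10 events per variable under a rule of thumb, or a wait of about one inclusion period. The main endpoint, a descriptive set of ventilation settings, is untouched. Severity is minor to moderate.

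The eight-year projection is not an error. It is a figure that runs from 16,800 to 20,400 under the 30% loss, according to an assumption on timing that the protocol leaves out.

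**What to change.** 1. In section 4.4, state that year 1 is expected to yield about 3,000 patients and 90 deaths, and that the 100 deaths for the first mortality model are expected in year 2, after about one further inclusion period.
2. In section 7.4, define an adequate sample size as a count of deaths in the group analysed: 100 for a 10-covariate model, applied separately to each age group. A total of 19,800 gives 3,300 patients per age group only if the six groups are of equal size, and about 100 deaths in each only if mortality is also 3% in each. A death count removes both dependencies.
3. In section 4.4, state the pattern of centre loss behind the eight-year figure, for example gradual loss reaching 30% by year 8. If the sponsor instead means 30% lost from the start, the figure becomes about 9.4 years.

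The cost is wording in two sections. The stated patient targets do not change, and even 9.4 years fits within the planned 10.

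### The 19,800 total for six age-group models is six times the single-model size, so it relies on an even split of deaths across the age bands that nothing in the protocol secures

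*Protocol*

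**What the plan says.** All the relevant figures are in Protocol 4.4 (Sample size calculation). The starting point is a logistic model for mortality in invasively ventilated children: "we estimate to need 100 events using the 10 event per variable of thumb", with "We aim to add 10 covariates to the model". The rate is introduced with "With a conservative estimate of overall PICU mortality of 3" percent, from which "3300 patients are needed for this analysis".

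The section then turns to age. The requirement is put this way: "to do the same analysis in these groups we need around 19.800 patients in total". The stated purpose is "To explore differences between age groups", and the six bands in question are "< 1 month, 1-11 months, 1-2 years, 3-6 years, 7-12 years, 13-18 years".

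Four other sections bear on the point:
- 4.2 admits any patient under 18 years and sets no number per age band.
- 4.3 excludes infants below 37 weeks of corrected age, which bears mainly on the youngest band.
- 5.3 samples patients 1:1 in large centers, but not by age.
- 7.4 makes each planned analysis conditional on having enough patients, without saying what is enough for an age band.

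**The concern.** If the same model is to be fitted separately in every band, the total has to be driven by the band expected to have the fewest deaths. Multiplying the single-model size by the number of bands sizes the study for the average band instead. The bands range in width from about one month to about six years, and recruitment takes whoever is admitted, so an even split of deaths cannot be taken for granted.

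The aggregate of 19,800 could therefore be reached, and the age analyses treated as ready, while some bands hold well under 100 deaths. A 10-covariate logistic model in such a band would break the protocol's own events rule, with unstable and overfitted odds ratios. Six separate fits also do not in themselves test whether an association differs by age. If the bands hold very different numbers of deaths, a factor could reach significance in one band and not in another merely because of band size.

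**Working it through.** **Inputs from Protocol 4.4.** 10 covariates; 10 events per covariate; 3% mortality; 3,300 patients per model; six age bands; about 19,800 in total. The protocol gives no patient shares or mortality by band, so those used below are assumptions, shown as a range.

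**1. Reproduce the plan's figures.**
- Deaths needed per model: 10 x 10 = 100.
- Patients per model: 100 / 0.03 = 3,333.3, rounded up to 3,334. The stated 3,300 is this figure rounded down.
- Total: 6 x 3,300 = 19,800, which matches exactly. Unrounded it is 6 x 3,334 = 20,004.

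**2. What 19,800 delivers at 3%.** Expected deaths are 19,800 x 0.03 = 594, or 594 / 6 = 99 per band on an even split. The gap between 99 and 100 is rounding and is not the issue.

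**3. Uneven bands at a uniform 3%.** For a band with share s of the patients, expected deaths are 19,800 x s x 0.03. The total needed for that band to reach 100 deaths is 100 / (0.03 x s).

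| Assumed share | Patients | Expected deaths | Deaths per covariate | Total needed for 100 deaths |
|---|---|---|---|---|
| 15% | 2,970 | 89 | 8.9 | 22,223 |
| 12.5% | 2,475 | 74 | 7.4 | 26,667 |
| 10% | 1,980 | 59 | 5.9 | 33,334 |
| 5% | 990 | 30 | 3.0 | 66,667 |

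**4. Higher uniform mortality m.** The smallest share that reaches 100 deaths within 19,800 is 100 / (19,800 x m):
- 3%: 16.8%
- 4%: 12.6%
- 5%: 10.1%
- 6%: 8.4%

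A higher rate creates some slack but does not remove the dependence on share. At 6%, a 5% band has 19,800 x 0.05 x 0.06 = 59 deaths.

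**5. Equal sizes are not required.** Bands of 2,000, 5,000, 4,000, 3,000, 3,000 and 2,800 patients (sum 19,800) with mortality of 5.0, 2.0, 2.5, 3.3, 3.3 and 3.6% give about 100 deaths each, at 600 / 19,800 = 3.03% overall. What matters is the product of size and mortality.

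**The case against.** Four arguments favor the protocol.

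- **The deaths may balance.** As step 5 shows, small bands with higher mortality can match large bands with lower mortality. A reader might infer that 19,800 works only if all six bands have the same size and the same 3% mortality. That condition is too strict. The argument stands against the strict reading. It does not rescue the figure, because the protocol gives no data to show that size and mortality do offset each other.
- **The 594 against 600 comparison proves little.** A reader might infer that it is arithmetically impossible for every band to reach 100. The six-death gap comes from rounding 3,334 to 3,300. Moreover, 594 is an expectation and not a cap: the binomial standard deviation is the square root of 19,800 x 0.03 x 0.97, about 24. The protocol also says that its total is approximate and calls 3% conservative. This argument stands in full.
- **Section 7.4 is a safeguard.** A reader might infer that small bands will certainly be modeled with too few events. The protocol does not say so, since analyses wait for enough patients. But 7.4 sets no threshold per band, and the only figure that 4.4 attaches to the age analyses is the aggregate. The safeguard exists in principle and is undefined where it is needed.
- **The analysis is exploratory.** Age differences are in neither the objectives (2.1) nor the hypotheses (2.2), the main endpoint is descriptive (5.1.1), and the single overall mortality model needs only 3,300 patients. Nothing says that age differences will be judged by comparing significance across bands, and 7.3 does not exclude interaction terms. This lowers the severity. It leaves the sample-size statement unsupported.

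**Conclusion.** The point holds in a limited form. The 19,800 figure is the size for six average bands. It secures about 100 deaths in each only under a roughly even split of deaths, which nothing in the protocol produces or supports, and it has no margin for an uneven one.

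The size of any shortfall cannot be established from the document. The figures of 89, 59 and 30 deaths illustrate assumed shares of 15, 10 and 5% at a uniform 3% mortality; they do not predict what any actual band will contain. A true rate above 3% would shrink the shortfall.

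Severity is moderate: an unsupported claim about an exploratory analysis, which leaves the main descriptive aim and the overall mortality model untouched.

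**What to change.** Three changes of wording:

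1. In 4.4, state that 19,800 supports the 10-covariate model only in bands expected to hold about one sixth of the deaths at 3% overall mortality, and that bands with fewer deaths will not meet the 10-events-per-variable rule.
2. In 7.4, define a sufficient size for an age-band model as 10 deaths per fitted parameter within that band, instead of the 19,800 aggregate.
3. Explore age differences with one pooled model of all invasively ventilated patients, with a pre-specified age-by-exposure interaction, and report age-specific estimates from it. As an illustration, 10 covariates including one linear exposure, plus five band indicators and five interaction terms, make 20 parameters, and 594 / 20 = 29.7 deaths per parameter. Estimates for sparse bands will still be imprecise, and their confidence intervals will show it.

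The cost is protocol and SAP text, with no extra patients. The downside is a less favorable claim for small age bands, some of which may not get a model of their own.

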#### 7.4. Planned analyses

This study will run for an estimated period of 10 years. If an adequate sample size is reached for a planned analysis, this analysis will be performed.

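### The 19,800 patients stated for six age-band mortality models are a best-case minimum: they give about 100 deaths per band only if deaths split equally over the bands

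*Protocol*

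**What the plan says.** Protocol section 4.4 sets its requirement in events: "we estimate to need 100 events using the 10 event per variable of thumb", together with "We aim to add 10 covariates to the model". It converts events to patients with a single overall rate: "With a conservative estimate of overall PICU mortality of 3% (1, 23) 3300 patients are needed for this analysis".

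It then turns to six age bands ("< 1 month, 1-11 months, 1-2 years, 3-6 years, 7-12 years, 13-18 years") and states that "to do the same analysis in these groups we need around 19.800 patients in total". The period of about eight years given for reaching that total, allowing for loss of centres, rests on this figure.

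Section 7.4 gives the only trigger for running an analysis: "If an adequate sample size is reached for a planned analysis, this analysis will be performed". It does not say whether adequacy is counted in patients or deaths, or in the whole cohort or the band.

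The protocol gives no expected share of patients, share of deaths or mortality for any band. Section 8.2 provides for inclusion of all ventilated patients. Section 5.3 samples eligible patients 1:1 in centres expecting more than 100 per period. Neither balances by age.

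**The concern.** The requirement is a number of deaths in each model, but the stated total is the one-model figure multiplied by the number of bands. That is correct only when every band supplies the same number of deaths. The bands range from 1 month to several years in width, no age-specific inputs are given, and nothing in the design would equalise them.

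Two things are at stake. First, 19,800 is presented as the number needed and supports the stated duration, yet on the plan's own inputs it is the smallest total that could work. Second, section 7.4 does not define adequacy, while section 4.4 states the age-band requirement as a total. A reader could therefore take all six models as licensed once the cohort reaches 19,800. A 10-covariate model fitted in a band well short of 100 deaths would breach the plan's own rule of 10 events per variable, and apparent age differences could partly reflect overfitting.

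**Working it through.** **Inputs (protocol section 4.4):** 10 covariates; 10 events per covariate; 3% mortality; six bands; 3,300 patients for one model; 19,800 for six. Share of deaths by band: not given, so every share below is an assumption.

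**Reproducing the plan's figures**
- Events per model: 10 x 10 = 100.
- Patients per model: 100 / 0.03 = 3,333, stated as 3,300.
- Six models: 6 x 3,300 = 19,800, which matches exactly (6 x 3,333 would be 20,000).

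**What 19,800 delivers**
- Expected deaths: 19,800 x 0.03 = 594.
- Equal split: 594 / 6 = 99 per band, which meets the target apart from the rounding of 3,333 to 3,300.
- Share of all deaths that a band needs to reach 100: 100 / 594 = 16.8%. An equal share is 16.7%, so there is no slack.
- The six counts must sum to 594, so if they are unequal at least one is below 99.

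**Size of the shortfall**

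Deaths in a band = 594 x share of deaths. Total needed = 100 / (0.03 x share).

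| Assumed share of deaths | Deaths at 19,800 | Deaths per covariate | Total for 100 deaths in that band |
|---|---|---|---|
| 1/6 | 99 | 9.9 | 20,000 |
| 14% | 83 | 8.3 | about 23,800 |
| 12% | 71 | 7.1 | about 27,800 |
| 10% | 59 | 5.9 | about 33,300 |
| 8% | 48 | 4.8 | about 41,700 |
| 5% | 30 | 3.0 | about 66,700 |

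**How many bands fall short** (assumed shares of deaths, youngest band first)
- 12% in one band, 17.6% in each of the others: 71 and five of about 105. One short.
- In proportion to band width, with 18 years as the upper limit: 3, 30, 66, 132, 198, 165. Three short.
- 14/22/18/16/16/14%: 83, 131, 107, 95, 95, 83. Four short.
- 10/35/20/13/12/10%: 59, 208, 119, 77, 71, 59. Four short.
- 20% in one band, 16% in each of the others: 119 and five of 95. Five short, though only slightly.

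The count therefore runs from one to five of six, depending on the split.

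**Can a short band catch up by year ten?** Planned accrual is 50 centres x 30 patients x 2 periods = 3,000 a year, leaving out the optional epidemic period.

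| Reading of the 30% loss of centres | Patients in 10 years | Deaths at 3% | Share of deaths needed for 100 |
|---|---|---|---|
| All lost from the start (x 0.70) | 21,000 | 630 | 15.9% |
| Building evenly to 30% (average x 0.85) | 25,500 | 765 | 13.1% |
| No loss | 30,000 | 900 | 11.1% |

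Extra time helps, but at 3% mortality a band with less than about 11% of deaths would not reach 100 on any of these readings.

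**The case against.** The strongest defence is that several steps from this figure to a failed analysis are not in the protocol.

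- **Most bands will miss the target.** A reader might infer this from the very different band widths. The protocol does not support it: it gives no age distribution, and width says little about how many ventilated children or deaths a band holds. The count short is one to five of six. This objection stands in full.
- **Patients and mortality must both be equal across bands.** They need not be. Only deaths must split equally, and mortality can offset patient numbers. At 19,800, a band with 10% of patients (1,980) reaches 100 deaths at 5.1% mortality, and one with 35% (6,930) at 1.4%. This stands, but the protocol gives no band-specific rates showing that such an offset occurs.
- **The 3% is called conservative.** It is an overall PICU rate, whereas the model concerns invasively ventilated children. Under an assumed split of 8/35/18/14/13/12% of deaths, four bands are short at 3% (594 deaths). Two are short at an assumed 4% (792 deaths; 63 and 95), and one at an assumed 5% (990 deaths; 79). Higher mortality would ease the problem, but 19,800 is itself built on 3%.
- **Small bands will be fitted with too few deaths.** This too might be inferred, but section 7.4 makes each analysis conditional, so a short band may be delayed or dropped. That stands as far as it goes. The condition is undefined, and the age-band requirement is stated only as an overall total.
- **The analyses are exploratory, and detail may sit in an analysis plan that is not shown.** This lowers the severity. It does not rescue the figure, which the protocol itself states and uses.

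**Conclusion.** The point holds in a limited form. The 19,800 reproduces exactly as 6 x 3,300 and is the minimum total under equal deaths per band at 3% mortality, not the number needed in general. With any unequal split at that rate, at least one band, and possibly several, falls below the required 100 deaths. The total required is then set by the band with the fewest deaths: about 27,800 if it holds 12% of them and about 66,700 if it holds 5%. Those shares are illustrations. The protocol gives none, so there is no single corrected number and no basis for saying how many bands will miss.

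This should be fixed rather than must be fixed: the age-band models are exploratory, the overall 3,300-patient model is untouched, and inclusion is expected to run for about ten years anyway because of the rarer types of support.

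**What to change.** - **Section 4.4:** describe 19,800 as the minimum under equal deaths per band at 3% mortality, and remove the implication that all six models are supported once that total is reached. If the sponsor has an expected age distribution of deaths, derive the total from the smallest band with 100 / (0.03 x share), and revisit the eight-year estimate to match.
- **Section 7.4:** for the age-band models, define adequate sample size as 100 deaths within the band.
- **Short bands:** state in advance which rule applies. Either the band is not modelled separately, or its model is limited to about one covariate per 10 deaths; a band with 59 deaths, for example, would carry about five covariates instead of 10.

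The cost is protocol wording only, with no extra data collection. The drawback is that the stated figure becomes less favourable and some bands may not get a full model of their own.
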